7.2 Data Collection

Patients: Potentially eligible patients will be sent a letter of introduction and explanation about the study. The letter will inform patients that they will receive a call about the study in the next few days and will include a telephone number to call if they wish no further contact. A week after letters are mailed, the research assistants will call patients who have not called the "opt out" number. The research assistants will explain the study and answer patients' questions about study requirements, potential risks, and compensation. If the patient is interested in joining, the research assistant will confirm eligibility. If the patient is eligible, the research assistant will review the study procedures, the informed consent document and HIPAA authorization, and obtain verbal consent and authorization.

The research assistant will then collect the data to calculate the participant's risk for having an advanced colorectal neoplasm (ACN). This involves confirming gender, age, and family history of colorectal cancer. The research assistant will ask the patient for their smoking history and calculate pack years (none, < 30 pack years; \geq 30 pack years). The research assistant will also ask the participant for their waist size (for men: under 37 $\frac{1}{2}$ in; 37 $\frac{1}{2}$ - 47 in; $>$ 47 in; and for women: < 34 $\frac{1}{2}$ in; 34 $\frac{1}{2}$ - 43 $\frac{1}{2}$ in; $>$ 43 in).

The research assistant will discuss with the participant which of the 3 options they prefer to access the decision aid and survey: (i) through the EHR patient portal, (ii) by email, or (iii) on a iPad at a primary care practice. Based on that discussion, the research assistant will send the participant the link to their survey and decision aid. The research assistant can be available by phone or in-person at the practice as needed to assist participants in accessing the survey and decision aids. The research assistant will encourage participants who choose to access the surveys and decision aid on their own device to do so in a quiet location free as possible from distractions.

The email sent to participants will review the study procedures, who to contact with questions, and the unique link to their survey in Qualtrics. When the participant clicks the link, they will be taken to Qualtrics and the baseline survey (T0). After the participant completes T0, Qualtrics is programmed to stream the appropriate decision aid for that participant. When the decision aid completes, the post-intervention survey (T1) will display. Following completion of T1, the participant will be automatically sent a confirmatory email thanking them for completing this part of the study, reminding them of the next study contact, and who to contact with questions.

The baseline (T0) and post-intervention (T1) surveys are planned to take about 10 minutes each to complete. The control decision aid is approximately 10 minutes long and the intervention decision aid is approximately 15 minutes long (see Appendix for T0 and T1 surveys).

Research assistants will start contacting participants approximately four days after the participant's provider visit to complete the post-provider visit (T2) survey. Research assistants will aim to start collecting the T2 data four days after the provider visit; however, if the patient requests contact sooner due to scheduling conflicts, the research assistant will contact the patient as requested. Research assistants will first attempt to collect the T2 data over the phone; however, if unsuccessful or if the participant prefers, the research assistant can email the participant a link to complete the survey online in REDCap.

The post-provider visit (T2) survey is planned to take about 15 minutes (see Appendix for T2 survey).

Research assistants will start contacting participants 6 months after study enrollment to complete the 6-month follow-up (T3) survey. Research assistants will first attempt to collect the T3 data over the phone; however, if unsuccessful or if the participant prefers, the research assistant can email the participant a link to complete the survey online in REDCap.

The 6-month follow-up (T3) survey is planned to take about 15 minutes (see Appendix for T3 survey).

The patient's medical record will be queried for documentation of colonoscopy, FIT, or another approved screening test within six months of study enrollment. Regenstrief Data Core will query the electronic health records (EHR) for screening uptake for both Eskenazi Health and IU Health patients. Research assistants will confirm discrepancies between query results and patients' self-reported uptake.

Providers:

The Regenstrief Data Core will query the EMR for orders for colonoscopy, FIT, or other approved CRC screening test entered by each provider for their enrolled patients. They will also query the EHRs for the read status for all the provider notifications that were sent. Demographic data will be assessed using the AMA Physicians Datafile.

8.0 Reportable Events

If a participant experiences an adverse event that occurs in greater frequency or severity than previously known, this will be reported to the IRB either as a prompt report if it meets reporting criteria, or at time of study closure.

9.0 Data Safety Monitoring

[name], principal investigator will have ultimate responsibility for monitoring the safety and security of the participants and data. [name] and his study team will engage in quality improvement practices beginning with development and then with ongoing review of study procedures. The Co-Investigators will be actively involved in quality assurance activities including monitoring of recruitment, adherence to eligibility criteria, adherence to study protocol, quality of data entry, and adherence to any adverse event reporting.

10.0 Statistical Considerations

Sample Size Justification: This trial is powered for the two primary hypotheses. For Aim 1, we expect exposure to either personalized message will increase uptake from 30%, which was the uptake at six months seen in our current PCORI project, to 40% and the combined effect to be additive (i.e. no interaction between the interventions). We believe a 10% increase in uptake is a minimally important difference to detect. An earlier study found that patients who viewed a personalized message about risk of colorectal cancer had a 9% higher uptake than did those who viewed a non-personalized message (CI-2).⁴¹ We believe our intervention will have greater impact, due to its encouraging low-risk individuals (50% of patients)⁷ to use a non-invasive test. An earlier study found that individuals due for screening who were offered a non-invasive test had a 31% higher rate of screening than those offered just colonoscopy (69% vs. 38%)(CI-2).⁵ To detect an effect of 10% increase (odds ratio of 1.55) with a power

of 80% (two-sided $\alpha=0.05$) a sample size of 732 subjects (183 per group) is needed for the Wald test for either patient or provider message main effect in a logistic model if patient outcomes were independent. To account for clustering due to randomization by provider, we inflate the sample size based on the design effect. We assume an intraclass correlation of .05 for provider, and average number of subjects per provider of 8. (RC-3) We will allow for an attrition rate of 10%. This results in a final sample size of 1100 (275 per group). For the informed choice outcome, we expect exposure to either personalized message would increase informed choice from 20%, the outcome in our current PCORI project, to 30% (odds ratio of 1.71) and the effect to again be additive. This leads to an initial sample size of 604 total (151 per group) before accounting for inflation and attrition, which is less than for uptake. Thus, the sample size needed for both outcomes is 1100 (275 per group, 130 providers). These recruitment goals are readily achievable based on the INFORM study. Aim 2 is considered exploratory because we don't have sufficient preliminary data to estimate all effect sizes; however, we will have sufficient power for some hypotheses. (IR-1)

Analytic plan: Preliminary analyses will compare baseline demographic information across the four groups using means and standard deviations for continuous variables and frequency distributions for categorical variables. We will adjust for those characteristics in subsequent analyses if significant differences emerge at a conservative level for inclusion of a covariate ($p<.20$). Characteristics of participants who don't complete T1 and/or T2 will be compared with those who remain to determine what biases may exist. The above analyses will be conducted using ANOVA, chi-square tests, or exact or non-parametric equivalents. If there appear to be biases in dropout, we will conduct pattern mixture models analyses to see how the results could change based on the missing data assumption (IR-5, MD-2, MD-3, MD-4). Primary analysis of outcomes will employ an intent-to-treat analysis. For Aim 1, our primary hypotheses will be tested using logistic regression models with the outcomes of informed choice and uptake (both yes/no outcomes) and main effects for: 1) patient receipt of personalized message; and 2) provider receipt of personalized message. A random effect for provider will be included to account for the clustered randomization. We will test for an interaction effect, but do not expect one so have not powered the study for an interactive effect. The secondary hypotheses (planned subgroup analyses with low risk group) will be tested using the same model type (HT-2, HT-3). The secondary hypotheses are considered exploratory. For Aim 2, mediation effects (RQ-6) will be estimated in a logistic regression setting, fitting the appropriate mediation models using MPlus⁷⁶ and then testing indirect effects using the percentile bootstrap approach to estimate the indirect effect.⁷⁷ For primary analyses, we will fit models that estimate the effects of either or both of the interventions relative to control. Moderators (RQ-4, HT-1, HT-2, HT-3, HT-4) will be identified by significant interaction terms in the regression models from Aim 1.

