- *Perceived Shared Decision Making* (T2) will be assessed with two measures. Patients will first answer five items adapted from the Shared Decision Making Process_4 Survey. This tool is a National Quality Foundation Measure used to assess the extent to which patients are involved in the decision-making process (PC-3, IR-4).⁵⁴ Patients will also respond to the 3-item CollaboRATE measure that assess three key areas of shared decision making; 1) explaining the health issue; 2)

asking for patient preferences; and 3) incorporating patient preferences into the decision. Each item uses likert response options ranging from “no effort was made” to “every effort was made”.^{73, 74}

- *Numeracy*: *Subjective numeracy* will be assessed at T0 with the Subjective Numeracy Scale (SNS) – short form, a validated instrument that involves 3 Likert-style questions.^{67, 71, 72}
- *Literacy* (T0) will be assessed using a 3-item health literacy scale (IR-4).⁷⁵
- *Demographic data* (T0) (including age, gender, income, education), as well as data on previous MD CRC screening recommendations, will be assessed utilizing a survey that has been used by our team and other researchers in multiple studies of CRC screening.^{51, 69}

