The research team will send potentially eligible patients a letter of introduction explaining the study (see Notes & Attachments for letter and brochure). The letter will also include a phone number that patients can call to opt out of being contacted. A week later, the research assistant will call patients (see Notes & Attachments for phone script) who have not opted out to explain the study and answer questions about study requirements, potential risks, and compensation. If the patient is interested in joining, the research assistant will confirm eligibility. If the patient is eligible, the research assistant will review the study information sheet (SIS) and HIPAA authorization. The SIS and HIPAA authorization will be emailed to the participant after the recruitment call with instructions and encouragement to contact the study team with questions. If the patient prefers, the research assistant can schedule a follow-up call to discuss the SIS and HIPAA authorization after the patient has had time to receive and review. For those patients who refuse to be assessed for eligibility, the RA will record reasons for refusal.

Participants will be offered three options to access the decision aid and complete the first two surveys (T0 and T1). They may choose to receive an electronic link: (i) through the EHR patient portal (preferred), (ii) by email, or (iii) on an iPad provided at the patient's clinic. For systems (i) and (ii), the research assistant will provide assistance as needed by phone when the patient opens the link or in the clinic for those who wish to use the iPad (method iii).

The electronic link will take the patient to a Qualtrics database. A randomization scheme, generated by our Biostatistics team, will be connected to the Qualtrics database. When the participant enters Qualtrics, this will trigger Qualtrics to assign them to the Control group (view the non-personalized DA) or the Intervention group (View the personalized DA).

Research team members interacting with the participants will be blinded to patient assignment. The patients will be blinded to assignment of their provider.

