Providers: The providers will be identified through each health system's provider directory, and confirmed and updated by the practice administrators. All eligible providers will be sent a letter and study information sheet explaining the study (see Notes & Attachments for letter and SIS), and be given the opportunity to let the research team know if they choose not to participate. Providers who agree to participate will be randomized to the Control group (receives a generic message) or the intervention

group (receives patient's ACN risk). The providers will be randomized based on a randomization scheme generated by our Biostatistics team.

The research team will not be blinded to provider assignment as they will need to know which notification to send. Providers will know that their patient enrolled in the study; however, the provider will be blinded to the patient's group assignment.

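### The p<.20 baseline screen chooses Aim 1 covariates by imbalance rather than prognosis, so the primary model is not fixed until arm-level data are seen; the power at stake is small

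*Combined protocol and SAP*

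**What the plan says.** All of this is in the combined protocol and SAP.

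- **The screen (section 10.0, Analytic plan).** "Preliminary analyses will compare baseline demographic information across the four groups". Then: "We will adjust for those characteristics in subsequent analyses if significant differences emerge at a conservative level for inclusion of a covariate", with the level given as p<.20. On the tests: "The above analyses will be conducted using ANOVA, chi-square tests, or exact or non-parametric equivalents". No provider term is mentioned for them.
- **The Aim 1 model (same section).** It has a main effect for each message. "A random effect for provider will be included to account for the clustered randomization". No baseline covariate and no stratification factor is named.
- **The candidate pool (section 3.2).** Demographic data are described as "including age, gender, income, education), as well as data on previous MD CRC screening recommendations". The word *including* leaves the list open. T0 screening intent is a separate measure in the same section. The ACN risk inputs are collected by the research assistant before the survey link is sent (section 7.2).
- **Allocation (section 6.0).** For patients: "When the participant enters Qualtrics, this will trigger Qualtrics to assign them to the Control group" or the intervention group. For providers: "The research team will not be blinded to provider assignment as they will need to know which notification to send".

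**The concern.** Under randomisation, the chance that a baseline variable passes a between-group test has nothing to do with how well it predicts uptake or informed choice. A strong predictor is usually left out, and a useless one sometimes enters. Adjustment in a logistic model helps when the covariate is prognostic, and the rule never looks at that.

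Two things follow. First, the composition of the primary model, and with it the exact odds ratio being estimated, is settled only after arm-level baseline data have been examined. Second, two variables that the plan itself treats as central are outside the listed demographics. The theoretical framework in section 3.0 runs through screening intent, and the secondary hypotheses in section 2.0 are defined by ACN risk. At stake are a pre-specified primary model and possibly a little power.

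**Working it through.** **1. The plan's own sample size.** Section 10.0 gives 732 before inflation, ICC .05, 8 patients per provider and 10% attrition. The design effect is 1 + (8 − 1) × 0.05 = 1.35. Then 732 × 1.35 = 988.2, and 988.2 / 0.90 = 1,098, against 1,100 stated. About 1,100 × 0.90 = 990 patients are analysed. The figure is reproduced and contains no allowance for covariates.

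**2. How often the screen selects one covariate.** A four-group test has 3 df, and its p<.20 cut-off is a chi-square of 4.642. If the covariate has ICC ρ within provider and the test ignores this, only the provider contrast is inflated, by L = 1 + 7ρ. The trigger rate is P(L·χ²₁ + χ²₂ > 4.642). The ρ values are assumptions.

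| Covariate ICC | L | Selected | Left out |
|---|---|---|---|
| 0 | 1.00 | 20% | 80% |
| .05 | 1.35 | 24% | 76% |
| .10 | 1.70 | 28% | 72% |
| .20 | 2.40 | 35% | 65% |

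Prognostic strength does not appear in the formula. With the 4 or 5 variables named in section 3.2, treated as independent and unclustered, the chance that at least one enters is 1 − 0.8⁴ = 59% or 1 − 0.8⁵ = 67%.

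**3. Cost in power, one covariate inside the pool.** Simulation: 4,000 trials per cell, 990 patients, 130 providers, outcome ICC .05, random-intercept logistic model. Covariate strength is an assumption (OR 1.5 or 2 per SD). Entries are power under the rule → power when always adjusting (%).

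| OR per SD, covariate ICC | Uptake: patient | Uptake: provider | Informed choice: patient | Informed choice: provider |
|---|---|---|---|---|
| 1.5, .05 | 92.2 → 92.7 | 83.4 → 84.0 | 97.8 → 97.8 | 89.8 → 90.6 |
| 1.5, .20 | 93.2 → 93.8 | 81.9 → 83.1 | 97.4 → 97.4 | 90.0 → 90.7 |
| 2, .05 | 93.3 → 94.2 | 84.6 → 87.0 | 97.0 → 97.4 | 90.4 → 91.5 |
| 2, .20 | 93.6 → 94.7 | 83.0 → 86.4 | 97.5 → 98.1 | 90.4 → 92.4 |

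The loss is 0.0 to 3.4 points, and every cell exceeds 80%.

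**4. The rule against a fixed set of T0 intent and ACN risk.** A second simulation (1,000 trials per scenario, uptake 30% to 40%, ICC .05 on the latent scale) screened four demographics at log-odds 0.15 per SD each. ACN risk was set at log-odds 0 in the first row and 0.2 in the others. All strengths are assumptions.

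| Log-odds per SD of T0 intent | Provider: rule vs fixed | Patient: rule vs fixed |
|---|---|---|
| 0 | 86.3 vs 86.0 | 93.2 vs 92.3 |
| 0.4 | 86.8 vs 87.9 | 93.3 vs 93.2 |
| 0.7 | 87.2 vs 89.2 | 93.4 vs 94.5 |
| 1.0 | 87.2 vs 90.8 | 92.6 vs 95.5 |

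The change runs from −0.9 to +1.1 points when intent is null or weak, which is within a Monte Carlo error of about 1 point, and reaches 2.9 to 3.6 points when it is strong.

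**5. Type I error.** Under the rule in the first simulation it was 4.2–5.6%. In the second it was 3.7% (patient) and 6.7% (provider), with Monte Carlo error about 0.7 points. The unadjusted model gave 3.4% and 6.7% there, so the provider figure does not come from the rule.

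**6. Movement of the odds ratio.** With outcome ICC .05, a marginal 30% vs 40% (OR 1.56) becomes 1.59 conditional on provider, and 1.62–1.66 with one covariate at OR 1.5–2 per SD. For 20% vs 30% (marginal 1.71) the values are 1.77 and 1.80–1.85. For scale, with 495 per arm and clustering ignored, the standard error of the log odds ratio is √(1/148.5 + 1/346.5 + 1/198 + 1/297) = 0.134, giving a 95% interval of 1.20–2.02 around 1.56.

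**The case against.** The strongest reply is that almost nothing is lost. The rule is a stated algorithm, not analyst discretion. Type I error holds, power stays above the planned 80%, and the fixed set shows no gain when intent is null or weak. That stands, and it limits the point to a modest one.

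The documentary case for the alternative covariates is also thin. Section 3.0 describes intent as something the messages raise, which is not evidence that T0 intent predicts uptake. Section 7.1 reports an earlier trial in which FIT intent rose more in one arm with no difference in six-month uptake. ACN risk defines hypotheses about which test is completed, and nothing says it predicts overall uptake. The demographic list is open and already holds age and gender, two of the five ACN inputs. The lack of a provider term in the screen is inferred from silence. All of this stands too, and a reader who infers that a fixed set is sure to add power goes further than the documents allow.

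A further objection is that removing the screen could leave a demographic imbalance unadjusted if recruitment differed by provider arm. This bears on the choice of replacement, so age and sex belong in the fixed set. A reader might also infer that recruiters select patients by provider arm. Section 6.0 says only that the research team is unblinded in order to send notifications. It does not say that those who recruit know the arm. If such an imbalance did arise, the screen could not tell it from chance.

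What the reply does not answer is why the primary model should depend on observed imbalance at all, when a fixed model needs no extra data.

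**Conclusion.** The point holds as a modest, inexpensive improvement. Selection is by imbalance: about 20% per covariate, up to about 35% if it clusters by provider and the test ignores this. The primary model is consequently unknown until arm-level baseline data are seen. The documents do not support the stronger readings that the rule inflates type I error through chance imbalance or leaves the trial underpowered.

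The power gain from a fixed set runs from about 0 points (null or weak prognosis) to about 3–4 points (strong). This rests on assumed covariate strengths and ICCs, because the documents give none, and the full set suggested below was not itself simulated. The main benefit is a model fixed in advance.

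**What to change.** 1. Delete the p<.20 rule. Name one short covariate set for all Aim 1 models from data already collected: for example T0 screening intent, ACN risk category, age, sex, health system and any stratification factor used in randomisation, with the provider random effect kept.
2. State the ACN levels. Section 7.1 has three for the piloted provider message and four for the current one. Very low risk is 8% of patients in section 1.0, about 0.08 × 990 = 79, so merging it with low in a covariate would cost little.
3. Handle missing T0 values by simple imputation or a missing indicator. Allocation precedes completion of T0 (sections 6.0 and 7.2) and questions may be skipped (section 12.0), so a complete-case model could drop randomised patients whose uptake is known from the EHR.
4. State that the adjusted odds ratio is conditional on provider and covariates, and also report a standardised risk difference. Keep the unadjusted model as a sensitivity analysis. The risk difference prevents non-collapsibility from being read as lack of robustness.
5. Report baseline data by group without tests.

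Cost: a few sentences in the analytic plan, a little more analysis work and a slightly different odds-ratio target. No added patients, visits or data items.

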3.1 Primary Outcome Measures

The primary outcomes are screening uptake and decision quality, each of which is essential to providing high-quality and patient-centered care.

- Screening uptake will be defined as performance of colonoscopy, FIT, or another approved screening test within six months after enrollment, as documented in the EHR.
- Decision quality will be defined by the multi-dimensional measure of informed consent (MMIC),⁵³ where a high-quality decision is one where the individual has adequate knowledge regarding the available options and undergoes the intervention that he or she has chosen or that fits his or her values (“value concordance”). (PC-3, IR-4)
 - Knowledge (T2) will be assessed by a 12-item test made up of 6 multiple choice questions and 6 true-false questions that was updated from what we used in our previous study to reflect changes in screening guidelines. Adequate knowledge = 9 correct
 - Concordance (T3) will be measure between the test choice at T2 and screening test underwent, if any, within six months after enrollment(T3).

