3.2 Secondary Outcome Measures

Patients: Data will be collected from patients at four time points: before they view the decision aid (T0); immediately after they view the decision aid (T1); aiming for 4-7 days after their appointment with their provider (T2); and six months after enrollment (T3).

- *Screening Intent* (T0, T1, T2): Intent to be screened for CRC with any test (“Screening Intent”), will be measured with 1 item: “Do you plan to get any type of colon test within the next 6 months?” and has a response option of: 5=Definitely, 4=Probably, 3=May or May not, 2=Probably not, and 1=Definitely not. This measure has been used in previous studies by our research team (PC-3, IR-4).^{51,52}
- *Test choice* (T0, T1, T2) (PC-3, IR-4): As in our previous studies:^{51,52}
 - For those who answer *Screening Intent* with “Definitely not,” “Probably not,” or “May or may not,” *Test Choice* is categorized as No screening.
 - Those who answer *Screening Intent* with “Probably” or “Definitely” have *Test Choice* categorized based on their answer to a single item: “If you have a colon test, which one would you choose?” Response options are: Stool test (FIT or Cologuard), Colonoscopy, Another test, or Don’t know.
- *Perceived CRC risk* (T0, T1, T2):
 - *Perceived personal CRC risk* will be assessed with a three-item scale, modified from items originally developed by Champion to measure perceived breast cancer risk^{78,79} and used by members of our team in multiple projects.^{51,52,69} Each item uses a four-point response option, where 1 = very unlikely and 4 = very likely, to assess participants’ beliefs about how likely they are to get CRC in the next 5 years, in the next 10 years and sometime during their lifetime. Cronbach alpha was 0.90 in our recent study. (PC-3, IR-4)
 - *Perceived comparative CRC risk* will be assessed with a single item measuring perceived comparative risk,⁶⁶ which asks “Compared to other women/men your same age, would you say your chance of getting colon cancer in the next 10 years is higher, about the same, lower, or don’t know?” (PC-3, IR-4)
- *Decision Conflict* (T0, T1, T2) will be assessed with the low literacy version of the Decision Conflict Scale, a ten-item instrument that assesses patients’ subjective feeling regarding the decision process over five areas and has been used widely in studies of decision aids (PC-3, IR-4).^{61,70}

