11.0 Statistical Data Management

We will create a secure web-based system to capture study data using the REDCap and Qualtrics database management system. We will review and process data using multiple verification and edit checking programs (e.g. range-checks, missing data reports). We will also conduct rudimentary analyses to ensure that the data have been properly collected and to identify any outliers or errors. A consort diagram will be constructed for reporting that accounts for all missing data (IR-5, IR-7, MD-1, MD-4).

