Confidentiality will be maintained by assigning each participant a unique identification number and using this number to identify the participant on all data collection forms. We will keep all paper documents locked in lockable cabinets in a locked office suite. Most of the data will be entered directly into REDCap or Qualtrics, HIPAA-aligned web environments. Processes and procedures have been documented and implemented to ensure the security and protection of the data within the computer operations centers, the servers, and the databases. Only those study team members who need access to this information will be allowed by the PI or study coordinator. All participants will be fully informed about the study prior to enrollment and be given the opportunity to decline to answer any questions or to discuss any issues they find troubling. They will be told that they can terminate participation at any time for any reason.

Research team members will be trained in procedures to allow participant to withdraw from the study. REDCap and Qualtrics surveys will allow participants to pass over questions and still continue through the remainder of the questions.

All study team members including those involved with the recruitment, informed consent process, and data collection will be adequately trained. Training will include passing of our institution's required Collaborative Institutional Training Initiative (CITI) modules and ongoing study-specific training from study personnel.

Any files that contain protected health information that might be created during the course of the study will be stored on department servers. The PI and project manager will coordinate with the Department IT staff to control access to these folders.

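### The only missing-data sensitivity analysis for informed choice depends on a dropout check that cannot detect the loss it is meant to guard against

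*Combined protocol and SAP*

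**What the plan says.** Section 3.1 builds decision quality from two parts, and both need T2. The knowledge part reads "Knowledge (T2) will be assessed by a 12-item test made up of 6 multiple choice questions", with nine correct as the cut-off. The concordance part reads "Concordance (T3) will be measure between the test choice at T2 and screening test underwent, if any". Screening uptake is taken from the EHR (sections 3.1 and 7.2) and needs no T2 survey.

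The analytic plan in section 10.0 states: "Primary analysis of outcomes will employ an intent-to-treat analysis". It fits logistic models to informed choice and to uptake, with a random provider effect. On missing data it says that the characteristics of patients who do not complete T1 and/or T2 "will be compared with those who remain to determine what biases may exist", and then: "If there appear to be biases in dropout, we will conduct pattern mixture models analyses to see how the results could change". No other missing-data sensitivity analysis is named. Section 11.0 adds a reporting step: "A consort diagram will be constructed for reporting that accounts for all missing data".

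**The concern.** The comparison of non-completers with completers uses what was measured on both groups. The plan gives no criterion for deciding that a bias has appeared, although the same paragraph sets p<.20 for covariate adjustment. It also describes no split of the dropout comparison by arm.

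The deeper problem is one of logic. Pattern-mixture models ask what happens if non-responders differ from responders in the unobserved outcome. Similar age, education or baseline intent does not show that T2 knowledge and choice are similar. A clean comparison would therefore cancel the analysis without having answered its question. One of the two modelled primary outcomes could then be reported with no account of how far it depends on the missing patients. The diagram in section 11.0 would count them but would not show that dependence.

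The direction of any bias cannot be assumed. Under section 3.2 a patient with low intent has a test choice that "is categorized as No screening", so an unscreened non-responder may be concordant.

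**Working it through.** **Inputs, all from section 10.0.** Informed choice 20% vs 30%; 732 patients before inflation (set by uptake); intraclass correlation .05; 8 patients per provider; attrition 10%; final size 1100, so 550 per side of each main-effect comparison.

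**The plan's own figure.** Design effect = 1 + (8 − 1) × .05 = 1.35. Then 732 × 1.35 / 0.90 = 1098, rounded to 1100. This reproduces. Dividing by 0.90 makes sense only if lost patients leave the analysed set, which is why the text implies a complete-case analysis.

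**Assumption for what follows.** The 10% attrition is T2 loss, equal on both sides: 495 of 550 respond. The plan does not say which loss the 10% refers to.

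**1. Effect of the rule alone.**
- Complete-case: 30 − 20 = 10.0 points; odds ratio (.30/.70)/(.20/.80) = 1.71.
- Missing counted as failure: .9 × 30 − .9 × 20 = 27 − 18 = 9.0 points; odds ratio (.27/.73)/(.18/.82) = 1.68.

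**2. Dependence on non-responders.** Let q0 and q1 be the informed-choice rates among non-responders without and with the message. The effect in all randomised patients, in points, is 0.9 × 10 + 10 × (q1 − q0).
- q1 = q0: 9.0.
- q0 = .30, q1 = 0: 6.0.
- q0 = 0, q1 = .30: 12.0.
- Logical limits (q0 = 1, q1 = 0 and the reverse): −1.0 and 19.0.

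**3. Tipping points.** Complete-case SE = sqrt(DE × [p0(1 − p0) + p1(1 − p1)] / 495), where DE is the design effect. For all randomised patients, use rates 0.9p + 0.1q and 550 per side. Non-responders are treated as observed, with q0 and q1 placed symmetrically about the mean responder rate. The gap q0 − q1 is widened until z falls below 1.96. The 7-point case (20% vs 27%) is a chosen illustration.

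| Responder effect | DE | Complete-case SE (points) | z | Gap at which significance is lost | q0 vs q1 there |
|---|---|---|---|---|---|
| 10 points | 1.35 | 3.18 | 3.15 | about 31 points | 40% vs 10% |
| 10 points | 1.0 | 2.73 | 3.66 | about 39 points | 44% vs 6% |
| 7 points | 1.35 | 3.12 | 2.24 | about 5 points | 26% vs 21% |
| 7 points | 1.0 | 2.69 | 2.61 | about 13 points | 30% vs 17% |

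The 1.35 rows apply to the provider message, which is randomised by provider. The 1.0 rows assume no clustering penalty for the patient message, which is assigned to individual patients (section 6.0).

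**4. The joint outcome.** The primary hypotheses are worded as a high-quality decision together with completed screening. An unscreened patient fails that outcome whatever T2 would have shown. Suppose responders' joint rates are 20% and 30% and non-responders' uptake is 30% and 40% (assumptions). Non-responders' joint rates then cannot exceed 30% and 40%, and the limits shrink to 9 − 10 × .30 = 6 points and 9 + 10 × .40 = 13 points.

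**The case against.** A reader might infer that the plan leaves the primary handling of missing T2 wholly open, to be chosen once the data are seen. The documents do not support that. The division by 0.90 and the comparison with patients who remain both point to complete-case analysis. What is missing is one sentence saying so, and a choice made after seeing the data is not shown.

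A reader might also infer a gap for skipped knowledge items, since "REDCap and Qualtrics surveys will allow participants to pass over questions and still continue". But a cut-off of nine correct out of twelve can be read as counting a skipped item as not correct, and the T2 survey is a separate attachment. That inference should not be pressed.

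The strongest objection concerns size. The planned effect withstands large differences between non-responders. Only an effect already near the significance boundary is fragile: at design effect 1.35, giving non-responders equal rates lowers the 7-point z from 2.24 to 2.13. The limits of −1.0 and 19.0 need informed choice of 100% in one arm's non-responders and 0% in the other's. Nor do the documents show unequal loss. The message arm has about five more minutes of decision aid and five extra T1 items, and the team knows the provider assignment. Against this, staff dealing with patients are blinded to patient arm, and patients to provider arm.

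All of this stands, and it lowers the severity. It does not rescue the trigger. The plan already names a suitable method, and the condition attached to it rests on information that cannot settle the question.

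**Conclusion.** The conditional trigger in section 10.0 is a defect for informed choice. It can cancel the only missing-data sensitivity analysis on evidence that does not bear on the unobserved outcome. EHR-based uptake is not affected by missing T2.

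Severity is low to moderate. If attrition is 10%, is T2 loss and is equal by arm, the choice between complete-case and missing-as-failure is worth one point, and a 10-point effect is fairly robust. A 7-point effect is not: its tipping gap is about 5 points for the provider message, and about 13 for the patient message if no design effect applies there. Non-responder rates are assumptions throughout, and the tipping points depend on their symmetric placement.

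**What to change.** 1. Delete the condition. Run the pattern-mixture analysis for informed choice in every case, with non-responder rates varied separately by arm over a range stated in advance (for example 0% to 40%), and report where the conclusion changes.
2. If the joint outcome of a high-quality decision and completed screening is analysed, score patients with no EHR-documented screening as not met, whether or not T2 exists. Do not apply this to stand-alone informed choice, where an unscreened patient may be concordant.

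A sentence confirming the implied complete-case rule would be a useful clarification. Multiple imputation is optional.

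Cost: no new data, and one extra sensitivity model to specify and report.
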